1.1 Background

Osteoporosis is a multi-factorial skeletal disease characterized by low bone mass and a structural deterioration of the macro and microarchitecture of bone tissue, leading to increased bone fragility and susceptibility to fracture [1]. Osteoporosis is considered a global public health concern, due to its prevalence worldwide. Yet its pathogenesis has not been clear. Osteoporosis affects numerous people, of both sexes and all races, and its prevalence increases as the population ages. Currently, it has been estimated that over 200 million people, including 75 million in the United States, Western Europe and Japan [2], have osteoporosis. Approximately 30% postmenopausal women are osteoporotic in the US and in Europe [2]. In China, an observational study has suggested a total of 54 million women aged 50 or above have osteoporosis, representing a prevalence of 27.3% in this affected population [3].

Osteoporosis is often called a 'silent disease'. Its diagnosis relies on a bone mineral density (BMD) value by dual-energy X-ray absorptiometry (DXA, DEXA) [1] and/or a proven fragility fracture at major skeletal sites [2, 3]. It has a significant clinical impact because of the association with an increased risk of fractures at major skeletal sites including the hip, the vertebrae, and the distal forearm. At least 40% of osteoporotic women [4] and 15-30% of men [5] experience one or more fragility fractures in their remaining lifetime. The combined lifetime risk of hip, forearm and vertebral fractures (VF) is 40%, being equivalent to the risk of cardiovascular diseases [6]. Moreover, an initial osteoporotic fracture by any type is a major risk factor for a new fracture [7, 8]. For instance, patients with a history of VF have a 2.3-fold increased risk of a future hip fracture and a 1.4-fold increase in risk of distal forearm fracture [8]. These fragility fractures lead to a substantial loss of quality of life [6, 9], an increased hospitalization [10, 11] and an excessive risk of mortality [12], and thus cause a tremendous socioeconomic burden. Currently, Chinese therapeutic guideline has recommended a routine screening program, consisting of blood chemistry, chest-waist spine radiology, and DXA, for the diagnosis and treatment of osteoporosis in various populations including postmenopausal women with or without other socioeconomic and/or clinical risks.

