2.2 Secondary Objective(s)

1. To investigate the prevalence of osteoporosis in community-dwelling postmenopausal women in China;
2. To identify risk factors for prevalent vertebral fractures in community-dwelling postmenopausal women in China;
3. To identify risk factors for densitometric osteoporosis in community-dwelling postmenopausal women in China.

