The subject's densitometric measurement will be performed by DXA onsite. Different DXA scanners from manufacturers including Hologic, Lunar and Norland will be used onsite upon availability. The BMD of three skeletal locations, the lumbar spine, the femoral neck, and the total hip, will be determined and presented as absolute value, T-score. The definitions of normal (≥ -1.0 SD compared to young adult women), osteopenia (between -1 to -2.5 SD compared to young adult women) and of osteoporosis (≤ -2.5 SD compared to young adult women) will be applied for both locations in the study, by assessing densitometric readings based on the World Health Organization(WHO)classification [41]. Reference databases for the calculation of the T-score include the National Health and Nutrition Examination Survey (NHANES) III database for the hip and the manufacturer's database for the spine [42]. The US reference database in DXA devices provided by the manufacturers has been adopted in local China's clinical practice [3] and validated in published Chinese studies [36, 39]. No

single local reference database will be applied for a recalculation of T-score due to its relatively smaller sample size and lack of an extensive validation across Asian populations.

DXA has been established as a reliable method providing acceptable precision and accuracy. For lumbar spine, coefficients of variation (CV) in measurements have been reported between 0.26 and 1.5% in short-term studies [43-46], and between 0.8 and 2.6% in long-term studies [43-46]. Precision results for spine phantom measurements using DXA were reported between 0.4 and 0.67% and in long-term studies between 0.23% and 1.0% [43, 45-47]. The DXA measurement for the lumbar spine has a satisfactory diagnostic profile in terms of sensitivity and specificity (ROC AUC 94%) [45].

DXA Quality Control

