In the study, vertebral fracture is defined as the presence of at least one vertebra morphometrically classified as grade 1, 2, or 3 on Genant's score as agreed by the both radiographic assessments in the study. Two (2) experienced radiologists who are blinded to the study will separately review the vertebral morphology and grade Genant's Score as per protocol. Radiologists will receive additional training to reduce variability between inter-observer interpretations. Prior to the study, each site will forward sample radiographs to the radiology coordination site for quality assessment and to check compliance with the protocol and technical standard. Intra- and inter-observer reliabilities will be tested using first 100 X-ray images from any study site before the adjudication starts. If there is a disagreement in terms of Genant's grading between two study radiologists, a third party radiological review will give a final decision.

The Genant semi-quantitative approach has been established a reliable and reproducible assessment in radiographic vertebral fracture. The intra-observer agreement for prevalent vertebral fracture was generally between 93 and 97% ($\kappa = 0.73 - 0.89$) [51], regardless of the radiologist's experience. As compared with reviewer's experience and other quantitative methods, an inter-observer agreement by difference in experience and method was between 92 and 94% ($\kappa = 0.65 - 0.74$) [51].

Definitions of Osteoporosis

In the study, osteoporosis is defined [3, 41] if the subject has at least one of the following as:

- A BMD T-score ≤ -2.5 in at least one of the anatomic sites including the lumbar spine, the femoral neck, and the total hip;
- A proven prior non-pathological fragility fracture.

A fragility fracture is defined as a fracture that occurred with minimal trauma at a typical site of osteoporotic fracture that would be unlikely to cause fracture in a non-osteoporotic adult. This assessment will be made based on self-reported fracture section included in the questionnaire and a review of medical history/documents/physical examination, or as suggested by the radiographic imaging in the study.

5 Study Flow Chart

Study Period:	Enrollment		Observation	Follow-Up
Visit Number/ Title:	Invitation#	Screening [△]	Study Visit**	Unscheduled Visit***
Study Day	NA	1	1	NA
Informed Consent		X		
Medical History [※]		X		
Inclusion/Exclusion Criteria		X		
Investigator-administered Questionnaire [¶]		X	X	
Physical Examination*				

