8.1.2.1 Prevalence of Osteoporosis

In the study, prevalence of osteoporosis in community-dwelling postmenopausal women in China will be investigated as a secondary objective. Descriptive statistics will be made to statistically address this objective. Point estimates (percentage) and corresponding 95% CI (exact binomial and Wilson score) will be presented for each analysis category and will be adjusted by age distribution in China [53]. Prevalence rates will also be given by age group and geographic region. A case with osteoporosis is counted based on the definition in Section 4.

The prevalence of osteoporosis will be presented as overall and by different diagnostic criteria and will be listed separately to allow an evaluation on the frequency distribution of each individual diagnostic setting in the study population.

The analysis of osteoporosis prevalence is displayed in the Table 8.1.2.1.

Table 8.1.2.1 Statistical Analysis Approaches on the Prevalence of Osteoporosis

Osteoporosis	Rate*	Estimate**	Frequency ***
Overall	Crude/Age-Standardized	Point and 95% CI	Percent
By DXA BMD [^]	Crude/Age-Standardized	Point and 95% CI	Percent
By Fragility Fracture [△]	Crude/Age-Standardized	Point and 95% CI	Percent & Cumulative

* Prevalence rates will be sub-analyzed by age group (50 – 54, 55 – 59, 60 – 65, 65 – 69, 70 – 74, 75 – 79, and 80+; and by < 65 and ≥ 65) and/or geographic region (North, South, Southeast, Southwest, and Central);
 ** Based on exact binomial distribution 95% CI and Wilson Score 95% CI;
 *** Calculation of frequency is relative to overall percent (100%);
 ^ the subject with a T-score ≤ -2.5 as suggested by a DXA measurement
 △ The subject with DXA measurement with a proven non-pathological major fracture as reported by the medical history or as suggested by radiology.

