8.1.2.2 Risk Factors for Radiographic Vertebral Fracture or Densitometric Osteoporosis

As secondary objectives, all possible factors including socioeconomic status, lifestyle and clinical parameters will be assessed to identify if they are the risk factors of a prevalent vertebral fracture or densitometric osteoporosis in Chinese postmenopausal women.

A two-step statistical modeling will be established to assess the potential risks against the response of analysis interest (dependent variable). Initially, a single logistic regression for bivariate analysis will be used to give a percentage tabulation presenting proportions of case (morphometric vertebral fracture or densitometric osteoporosis) versus control by each analysis parameter. An odds ratio and associated probability (P value) will be given to examine the statistical significance of this independent variable in the model. A P value of 0.25 or less will be the criterion [54] for an entry into a multivariate logistic model for all estimated variables. Also, all clinically relevant variables, regardless of a probability level, will be included in the final model at the discretion of the study team.

Finally, a multivariable logistic regression model will be constructed for both dependent variables. A stepwise backward method to eliminate non-significant variables will be performed until all remaining variables in the model have a P value less than 0.1. The goodness-of-the-fit will be evaluated by using deviance and likelihood ratio tests and Hosmer–Lemeshow test [55] to assess if there is any single important variable missing from the model.

In the bivariate and multivariate analysis, age, BMD, and BMI will be fitted as continuous variables. Geographic region grouping study sites will be fitted as a categorical variable. Due to potential collinearity of BMD to vertebral fracture, BMD will also be introduced as a dichotomous variable (osteoporosis vs. normal and osteopenia). BMI may vary among study sites in the study, odds ratio per unit BMI instead of per standard deviation to minimize the biases upward.

8.1.3 Exploratory Objective(s): Calculation of Epidemiological Measure(s) of Interest (e.g. hazard ratios, incidence rates, test/retest reliability)

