8.3 Sample Size and Power Calculations

The sample size of the study was calculated based on prevalence data per age group several large epidemiological studies [29-32, 36]. As the prevalence of vertebral fractures increases with age, the sample size will be determined as per age group by setting a lower limit for each assumed age-based prevalence rate (Table 8.3.1), using Clopper-Pearson exact method [52] to compute the lower bound of the corresponding 95% CI at a 5% precision. A sample size of 545 at each geographic region will be statistically sufficient to cover all age groups in detecting the prevalence of vertebral fractures, assuming a 5% withdrawal rate for the spinal radiographs in the study. Considering geographic distribution (5 regions), a total sample size of approximately 2700 postmenopausal women aged 50 or above will be enrolled for the study. In addition, this sample size will yield a generally over 90% power at a 0.05 significance level to detect a geographic impact for the fracture prevalence by an odd ratio at 1.40 or 1.50, by using a univariate logistic model in estimating the change in probability.

Assuming a 40% nonresponse rate in population-based studies [56] and 5% ineligibility rate [32], invitation letters will be posted to approximately 4750 women in all regions.

Table 8.3.1 Sample Size Calculation by Age Group based Prevalence

Age group	Sample size	Assumed Prevalence	95% CI Lower Limit
50 - 54	44	5.0%	1.0%
55 - 59	81	7.0%	3.0%
60 - 64	100	12.0%	6.0%
65 - 69	90	16.0%	10.0%
70 - 74	80	20.0%	12.0%
75 - 79	70	23.0%	15.0%
>80	53	37.0%	26.0%

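### Risk factors for densitometric osteoporosis are sought only through the T-score cut; a supportive linear model on the lowest T-score would recover precision at almost no cost

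*Combined protocol and SAP*

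**What the plan says.** Section 2.2 states the third secondary objective: "To identify risk factors for densitometric osteoporosis in community-dwelling postmenopausal women in China". The footnotes to Table 8.1.2.1 count a densitometric case as "the subject with a T-score ≤ -2.5 as suggested by a DXA measurement". Section 4 (Definitions of Osteoporosis) lets any one of three sites qualify: "A BMD T-score ≤ -2.5 in at least one of the anatomic sites including the lumbar spine, the femoral neck, and the total hip".

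The underlying measurement is continuous. Section 4 (BMD Measurement) says that BMD at the lumbar spine, femoral neck and total hip "will be determined and presented as absolute value, T-score".

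Section 8.1.2.2 screens each candidate by one-variable logistic regression (entry at P ≤ 0.25). Then "a multivariable logistic regression model will be constructed for both dependent variables", with backward elimination until every remaining variable has P < 0.1. It also lets the study team keep clinically relevant variables whatever their P value. Continuous BMD appears there only on the explanatory side: "age, BMD, and BMI will be fitted as continuous variables". Section 8.1.3 again uses logistic regression for densitometric osteoporosis, and Section 8.1.4 only summarises BMD. No model in Section 8 has BMD or T-score as the response.

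**The concern.** Under the case/control coding, a woman at -2.4 counts the same as one at +1.0, and a woman at -2.6 the same as one at -4.5. The cut is needed to count prevalence. It is not needed as the sole response when the task is to find which characteristics go with low bone density, and it throws away measured information.

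The loss matters because variables are kept or removed largely by P value. Lower power means that a real factor is more likely to fall out of the final model. The exposure is greatest for factors that are uncommon or weak.

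**Working it through.** **Inputs from the documents**
- N: "a total sample size of approximately 2700 postmenopausal women aged 50 or above will be enrolled for the study" (Section 8.3).
- Osteoporosis prevalence in women aged 50 or above: 27.3% (Section 1.1, "representing a prevalence of 27.3% in this affected population"). This is a background figure, not a design input.
- Retention level: P < 0.1 (Section 8.1.2.2).
- Odds ratios 1.40 and 1.50 (Section 8.3). They are planning values for a regional effect on vertebral fracture, and are borrowed here only as reference points.

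**Assumptions (not in the documents)**
- The 5% radiograph withdrawal rate also applies to DXA.
- Exposure frequencies run from 5 to 50%; OR 1.2 and 1.3 represent weaker factors.
- The T-score is normal with a constant shift in exposed women.
- Covariates and clustering are ignored.

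**The plan's own figure.** The age-group sizes in Table 8.3.1 sum to 44+81+100+90+80+70+53 = 518. Then 518/0.95 = 545, as stated per region, and 5 × 545 = 2725, close to the stated 2700. Evaluable N = 2700 × 0.95 = 2565. The plan states no power for objective 3, so there is none to reproduce.

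**Information kept by the cut.** For a normal outcome and small effects, the relative efficiency is φ(z)²/[p(1−p)], where z is the normal quantile of the prevalence p.

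| Prevalence | Calculation | Kept | Lost |
|---|---|---|---|
| 27.3% | 0.3325²/0.1985 | 0.557 | 44% |
| 35% | 0.3704²/0.2275 | 0.603 | 40% |
| 40% | 0.3863²/0.2400 | 0.622 | 38% |

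At 27.3%, the logistic analysis of 2565 women carries roughly what a linear analysis of 2565 × 0.557 ≈ 1430 women would.

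**Power at P < 0.1, one example (exposure 10%, OR 1.40, prevalence 27.3%)**
1. Solve for the two group risks: unexposed 0.2659, exposed 0.3365. Check: 0.9 × 0.2659 + 0.1 × 0.3365 = 0.273.
2. Logistic: SE(ln OR) = √[1/(256.5 × 0.3365 × 0.6635) + 1/(2308.5 × 0.2659 × 0.7341)] = 0.140. Power = Φ(0.3365/0.1403 − 1.645) = 77%.
3. Linear: shift = 0.625 − 0.422 = 0.203 SD; SE = √(1/256.5 + 1/2308.5) = 0.0658. Power = Φ(0.203/0.0658 − 1.645) = 93% (92.5%).
4. Loss: about 15 points.

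**The same method across the range** (prevalence 27.3%; logistic % / linear % / loss in points)

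| Exposed | OR 1.2 | OR 1.3 | OR 1.40 | OR 1.50 |
|---|---|---|---|---|
| 5% | 24/33/9.5 | 39/54/15.5 | 54/73/18.3 | 69/86/17.0 |
| 10% | 36/51/15.3 | 58/78/19.3 | 77/93/15.1 | 90/98/8.3 |
| 20% | 52/72/20.1 | 79/94/15.2 | 94/99/5.9 | 99/100/1.4 |
| 30% | 61/81/20.7 | 87/98/10.8 | 97/100/2.6 | 100/100/0.4 |
| 50% | 66/87/20.8 | 90/99/8.6 | 98/100/1.6 | 100/100/0.2 |

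At 40% prevalence, the 10% exposed, OR 1.40 cell becomes 82% against 94%, a loss of about 12 points.

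**Check on the any-of-three-sites rule.** A simulation assumed site correlations of 0.6, 0.6 and 0.85, 20% exposed, prevalence 27.3% and a 0.15 SD shift. At two-sided 0.05 it gave 69% power for logistic regression, 91% for linear regression on the lowest T-score and 86% for linear regression on a single site. The gain therefore survives the composite definition.

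**The case against.** **The cut is the objective.** Section 2.2 asks about densitometric osteoporosis, a diagnostic category, and logistic regression on T-score ≤ -2.5 estimates exactly that. This stands. A reader might infer that the logistic model is wrong, or that the linear model should take over variable selection. The documents support neither. A linear model estimates a mean T-score shift: it could select a factor that acts only far from the cut and miss one that acts mainly in the low tail.

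**There is a safeguard.** The clause keeping clinically relevant variables regardless of P value could protect obvious candidates such as glucocorticoid use, smoking or parental osteoporosis, all of which are on the questionnaire list. This stands in part. The clause is left to discretion, and Section 8.1.2.2 does not say how it works alongside backward elimination. It reduces the risk of missing a real factor but does not remove it. Nor does the plan say that an unselected variable will be reported as not being a risk factor; the one-variable step also gives an odds ratio and P value for each.

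**The size is not a property of the plan.** A reader might take a loss of 10 to 20 points as general. It is not: at the borrowed odds ratios of 1.40 to 1.50 it needs uncommon exposures, and otherwise it needs weaker effects. The 44% figure also depends on prevalence. Table 8.3.1 places 293 of 518 women (57%) at age 65 or over, and any of three sites qualifies, so prevalence here may exceed 27.3% and the loss would be somewhat smaller.

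**A separate SAP is promised** in Section 8.1 and is not available. That logistic regression is the only analysis can be said of Section 8 alone.

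**Conclusion.** The point holds as a missed supportive analysis, not as an error or a contradiction. Within Section 8, objective 3 rests on the dichotomised T-score alone. That costs about 44% of the information at 27.3% prevalence and 38 to 40% at 35 to 40%, given a normal T-score.

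The power cost at the plan's retention level depends on effect sizes and exposure frequencies that the plan does not give. It is about 15 to 18 points for OR 1.40 and 8 to 17 for OR 1.50 with 5 to 10% exposed. It is 9 to 21 points for OR 1.2 to 1.3 with 5 to 50% exposed, and about 6 points or less for OR 1.40 to 1.50 with 20% or more exposed. These figures also assume a constant shift and 2565 women with usable DXA. The label is a cheap improvement.

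**What to change.** In Section 8.1.2.2, and in the separate SAP when it is written:

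- Keep the logistic model as the analysis of densitometric osteoporosis.
- Add a pre-specified, supportive multivariable linear regression of the lowest of the three T-scores, the quantity from which the ≤ -2.5 cut is taken. Use the same candidate covariates but leave out BMD. Report its coefficients beside the odds ratios.
- State that a factor clearly associated with T-score will not be described as unrelated to bone density merely because it dropped out of the logistic model.
- Leave the cut in Section 8.1.2.1 unchanged for prevalence.

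The cost is one paragraph and one more regression on data already collected. The downside is that the linear coefficient is a mean T-score shift and not an effect at the diagnostic cut. The constant-shift assumption should therefore be checked through the residuals, and both results shown.

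### The plan does not keep BMD out of the densitometric-osteoporosis model, although that outcome is itself a cut-off on BMD

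*Combined protocol and SAP*

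**What the plan says.** Secondary objectives 2 and 3 (Section 2.2) are to find risk factors for vertebral fracture and, separately, for densitometric osteoporosis. Section 8.1.2.2 covers both with a single procedure.

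- Each candidate is first tested alone. The entry rule is: "A P value of 0.25 or less will be the criterion [54] for an entry into a multivariate logistic model".
- Then "a multivariable logistic regression model will be constructed for both dependent variables". Backward elimination "will be performed until all remaining variables in the model have a P value less than 0.1".
- On the form of the covariates: "In the bivariate and multivariate analysis, age, BMD, and BMI will be fitted as continuous variables". The sentence names no outcome.
- A later sentence adds a second form: "Due to potential collinearity of BMD to vertebral fracture, BMD will also be introduced as a dichotomous variable", contrasting osteoporosis with normal and osteopenia combined.

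Section 4 defines the measurements. Under BMD Measurement: "The BMD of three skeletal locations, the lumbar spine, the femoral neck, and the total hip, will be determined", and the T-score comes from these readings. Under Definitions of Osteoporosis, the densitometric criterion is "A BMD T-score ≤ -2.5 in at least one of the anatomic sites". The footnote to Table 8.1.2.1 uses the same threshold. Section 8.1.2.2 does not say which site's BMD enters a model.

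**The concern.** In the fracture model BMD is a legitimate candidate. In the densitometric-osteoporosis model it is the quantity that was thresholded to make the outcome. With BMD in that model, the adjusted odds ratio for smoking, BMI or glucocorticoid use describes the link between that factor and crossing the T-score threshold among women with the same BMD. Secondary objective 3 asks which factors go with low BMD in the first place.

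A real risk factor can then lose its association and be eliminated. Depending on which site is entered and where the factor acts, it can also look stronger than it is, or protective. The final step of the risk-factor analysis for objective 3 would be misleading.

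**Working it through.** **1. What the text implies.** The plan gives no figure on this point, so there is none to reproduce. The first step of 8.1.2.2 defines a case as either outcome, the model sentence covers both, and the BMD sentence that follows carries no restriction. No text in the protocol excludes BMD from the osteoporosis model. A separate SAP is promised in Section 8.1 but is not among the documents.

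**2. What the adjusted odds ratio then measures.** Let T1, T2, T3 be the T-scores at the three sites. The outcome is y = 1 if min(T1, T2, T3) <= -2.5, and each T-score is a rescaling of that site's BMD.

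- *All three sites entered:* given T1, T2 and T3, y is fixed. No other factor can carry information about it.
- *One site entered, say T1:* if T1 <= -2.5, y is already 1. Otherwise another factor can matter only through the remaining two sites, given T1. If the factor lowers T1 alone, an exposed woman with the same T1 as an unexposed one tends to have better bone elsewhere, so the odds ratio can fall below 1.
- *Dichotomised BMD:* if defined on any site, it equals y. When tried, the fit failed through perfect separation, as it also did with the lowest-site T-score as covariate.

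**3. Illustration of size.** From the documents:

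- n = 2,700 x 0.95 = 2,565 (Section 8.3; the 5% there is for radiographs and is assumed here for DXA);
- age mix from Table 8.3.1;
- prevalence set to 27.3%, the osteoporosis figure in Section 1.1, used as an assumption.

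Assumed, not in the documents:

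- a binary factor with exposure 8% or 20%, lowering T-score by 0.3 or 0.5;
- spine-hip residual correlation 0.5, 0.65 or 0.8 (within hip 0.8, 0.85, 0.9);
- residual SD 1.2 at the spine and 0.95 at the hip sites;
- age slope -0.03 (spine) and -0.045 (hip sites) per year; BMI slope 0.07-0.08 per unit;
- T-score standing in for BMD.

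This gives 2 x 2 x 3 = 12 combinations for each of three patterns of action, 36 in all, with 300 datasets each. The logistic models contain the factor, age and BMI, plus the BMD terms shown. Ranges of the adjusted odds ratio:

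| Factor acts on | No BMD | One site, affected | One site, unaffected | All three sites |
|---|---|---|---|---|
| All sites equally | 1.62-2.42 | 1.01-1.73 | not applicable | 0.96-1.06 |
| Spine only | 1.27-1.61 | 0.54-0.83 | 1.48-3.18 | 1.04-1.53 |
| Hip sites only | 1.37-1.81 | 0.54-0.87 | 1.80-5.34 | 1.03-1.78 |

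One combination in full (effect 0.5, exposure 20%, correlation 0.65):

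| Factor acts on | None | Spine | Femoral neck | Total hip | All three |
|---|---|---|---|---|---|
| All sites | 2.32 | 1.64 | 1.22 | 1.23 | 1.01 |
| Spine only | 1.57 | 0.67 | 2.33 | 2.32 | 1.20 |
| Hip sites only | 1.79 | 3.33 | 0.71 | 0.70 | 1.27 |

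Monte Carlo 95% error, checked in 12 combinations, is about 2-6% of an odds ratio. Unadjusted first-step odds ratios were 1.25-2.18 and do not depend on BMD. In every run each BMD site alone met P <= 0.25, and every adjusted model with BMD had at least one BMD term at P < 0.1.

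**4. Effect on the P < 0.1 rule.** A repeat of the example gave 2.35 without BMD, 1.25-1.68 with one site and 1.02 with all three for the all-sites factor. That factor met P < 0.1 in 100% of runs without BMD and in 13% with all three sites. The spine-only factor fell from 1.58 to 0.66 once spine BMD was entered.

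A separate simulation used other assumptions: n = 2,700, 100 runs, mean T-score -1.3, residual SD 1, shifts of -0.35 per SD of age and +0.30 per SD of BMI, and between-site correlation 0.5, 0.7 or 0.85, giving prevalence 21-27%.

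| BMD in model | OR per SD of age | Age at P < 0.1 |
|---|---|---|
| None | 1.87-1.96 | 100% of runs |
| One site | 1.42 / 1.30 / 1.18 | 100% / 98% / 58% |
| All three | 1.00-1.01 | 6-13% |

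With all three sites, age is retained about as often as the 10% expected by chance.

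**The case against.** The strongest reply is that BMD was meant for the fracture model only. The quoted sentence sets functional form and is not a covariate list. The one reason given for special handling of BMD concerns vertebral fracture, and the dichotomised term would make the osteoporosis model impossible to fit. That reading is plausible. But the dichotomising sentence adds a form of BMD and removes none, and the continuous term would run without any warning sign.

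Three safeguards might be claimed. The promised SAP could settle the matter, but nothing supplied shows that it does. Section 8.2.1 says methods will be chosen to avoid bias involving BMD, but excludes nothing. Section 8.1.2.2 also provides that "all clinically relevant variables, regardless of a probability level, will be included in the final model at the discretion of the study team". This allows variables to be added; keeping a factor in the model does not correct an odds ratio that is conditional on BMD.

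Several limits on size do stand.

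- The 36-combination simulation used fixed models and did not run the full backward elimination.
- The 27.3% is not this study's any-of-three-sites prevalence.
- Reversal appeared only when a factor acted on one region and BMD from that region alone was entered. The plan supports neither condition, and with all three sites the site-specific odds ratios stayed above 1.
- A factor acting equally on all sites showed attenuation only.

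**Conclusion.** The concern holds. Read literally, Section 8.1.2.2 puts BMD into a model whose outcome is a threshold on BMD, and no other text prevents it. The circularity follows from the definitions in Section 4 and needs no simulation.

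The size is illustrative. For a factor acting equally on all sites, the association is weakened with one BMD site and essentially gone with all three. Inflation or reversal depends on site-specific action and on the site entered.

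Only the adjusted odds ratios for secondary objective 3 are affected. Because the intent may have been sound, this is a specification to correct before analysis rather than a flaw in the design. The unnamed BMD site in the fracture model is a smaller gap of missing detail.

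**What to change.** State in Section 8.1.2.2, and repeat in the separate SAP, that BMD in any form (continuous, T-score or category) and any variable calculated from it are excluded from the densitometric-osteoporosis model. This includes FRAX calculated with BMD, since Section 4 lists FRAX with and without BMD among the analysable variables. State also that BMD is a candidate only in the vertebral-fracture model, and name the site or sites used there.

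The cost is one or two sentences. No new data, change in conduct or additional model is needed.
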